- Hematology or other patients in the infusion center
- Patients who have previously received more than 2 sessions of CAT in the infusion center
- Non-English speaking patients

3. Study Design

A repeated measures design will be used with each patient serving as his/her own control.

Any Oncology patient in the CCBD who has not previously received more than two sessions of CAT in the outpatient unit and who will be receiving approximately weekly infusions of at least one hour in the infusion center will be identified by a research assistant. The study will be explained to the patient/family and informed consent will

be obtained by the principal investigator or the research assistant. A demographic form will be completed including the information of diagnosis, age, treatment, educational level of parents, zip code, prior experience with art, music, movement.

The intervention will consist of approximately weekly CAT in the infusion center during cancer therapy. The interventionist is a Master's prepared, licensed dance/movement therapist who is experienced in music and art therapies as well. The CAT includes dance/movement such as playing with a parachute, simple yoga breathing and postures, and work with physioballs. The music includes singing, listening to music, and playing instruments. The art consists of drawing, finger painting, working with clay. The CAT may occur in individual sessions in private infusion rooms, or in groups in the middle of the infusion center. The CAT is not only a distraction, but also a therapeutic process addressing the stressors of cancer and its treatment. The "dose" of CAT will be recorded (number and type of sessions) and will be factored into the analysis.

The subjects and/or parents will be tested with all instruments before the intervention, and approximately every 30 days for no less than 3 months and a maximum participation of 6 months. Treatment time points will be at least 30 days apart. Because some subjects are not scheduled to come into the clinic every 30 days for SOC appointments, they are unable to complete 3 sessions of CAT in a 3 month time period. For those subjects who are scheduled to come into clinic every 1-2 months for SOC appointments, study participation may take up to 6 months. This 6 month time period would allow for the completion of 4 different time points of CAT.

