The testing will take place in an exam room after vital signs have been completed upon intake to the clinic. The trained research assistant, trained RN, or PI will administer the questionnaires. The PedsQL includes a subject report (ages 5 and over) and a parent report. The Resilience Scale is a self-report and will be used for ages 12 and over. The Faces Scale will use parent report for ages less than 5 and self-report for ages 5 and over. In order to confirm consistency, the posture measure will be completed by the PI (nurse practitioner) or registered nurse on the study after training with the manual included with the inclinometer tool.

Off Study Criteria

1. Subject discontinues CAT
2. Unable to complete 4 time points in 6 months

C. Description, Risks and Justification of Procedures and Data Collection Tools

The anticipated risks include psychological distress incurred by completing the outcome measure questionnaires as well as the therapeutic process. This risk will be minimized by the presence of the Master's prepared, experienced dance/movement therapist. The patients' social workers through the clinic will be available during the intervention as well.

D. Potential Scientific Problems

Based on the pilot data, the anticipated scientific problem is slow accrual due to unforeseen events during the traumatic time of a new diagnosis in pediatric oncology. We are unable to randomize because CAT is standard of care for any patient in the infusion center and therefore we feel it is unethical to deny CAT to a control arm. Therefore, we will compare the subjects to themselves over time to look at longitudinal changes of CAT.

E. Data Analysis Plan

The primary outcome is Peds QL at approximately 3 months; secondary outcomes will be the Resilience Scale, Faces Scale, and postural measurement at approximately 3 months. A repeated measures analysis of variance will be used to analyze the primary and secondary outcomes. We will also use the repeated measures analysis of covariance with the addition of covariates, depending on their statistical significance, such as gender, age, cancer diagnosis, and previous exposure to arts/music/dance. All of the analysis will be adjusted for baseline measures.

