We expect to recruit 100 patients, we also expect patients will be equally distributed in the following 3 categories: receiving low (0-3), intermediate (4-6) and high (7+) CAT sessions due to the nature of each patient's random visits. Power analysis was done based on pair-wise T-Test with these assumptions for simplicity. With 33 patients in each group, assuming 80% power and 0.017 significance level of alpha after Bonferroni ad justification of multiple comparisons, we will observe a minimum effect size of 0.813. This is to say that 80% of the Peds QL scores in the lower session CAT group will be below the average of scores in the higher session CAT group. Thus, what we would expect to see in the positive dose-response relationship.

We will also conduct subgroup analysis by age group if the sample size is large enough since Peds QL is designed by age group.

F. Summarize Knowledge to be Gained

Integrative and holistic therapies are being used throughout healthcare. We know that families are using alternative therapies without rigorous evidence documenting their worth. We therefore strive to build a body of literature showing evidence that CAT helps children with cancer feel better.

G. Appendices

1. PedsQL
2. Resilience Scale
3. Faces Scale
4. Inclinator information
5. Patient/Family Survey

H. References:

- Bhat SR, et al. (2005) Profile of daily life in children with brain tumors: an assessment of health-related quality of life.[see comment]. *J Clin Oncol*, 23, 5493-5500.

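### Followed as named, the off-study criteria and repeated measures ANOVA give in effect a completers' 3-month PedsQL change, which selective loss could bias in either direction by an unknown amount

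*Combined protocol and SAP*

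**What the plan says.** The Off Study Criteria in Section IV.B are two: "Subject discontinues CAT" and "Unable to complete 4 time points in 6 months". Section IV.B.3 has children tested before the intervention and then "approximately every 30 days for no less than 3 months and a maximum participation of 6 months". It explains the longer window as allowing "completion of 4 different time points of CAT" for children seen in clinic only every one to two months.

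Section IV.E states: "The primary outcome is Peds QL at approximately 3 months". It continues: "A repeated measures analysis of variance will be used to analyze the primary and secondary outcomes". Covariates may be added in an ANCOVA, and all analyses are to be adjusted for baseline. Section IV.D gives the basis of inference. There is no control arm, so "we will compare the subjects to themselves over time".

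The documents do not define an analysis set, the handling of missing visits, the estimation method or a sensitivity analysis for loss. They also do not say that scores collected before a child goes off study are thrown away.

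**The concern.** Repeated measures ANOVA in its standard form needs a full set of visits from each child and drops any child who lacks one. The off-study criteria create children with incomplete visits, and they do so for reasons that may be related to how the child is doing: stopping the therapy, or not attending often enough. Taken together, the two sections let the primary result describe only the children who stayed.

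In a randomised comparison, similar loss in both arms may partly cancel. Here there is nothing to cancel against, because the estimate is the average change within children. If children who get worse after starting CAT tend to leave, those who remain look improved. If children with low baseline scores tend to leave, the rise they would have shown through regression to the mean is lost, and those who remain look worse.

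Leaving early also lowers a child's session count, so how leavers are placed in the session categories of Section IV.E should be visible to the reader.

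**Working it through.** **The plan's own figure.** Section IV.E gives a minimum effect size of 0.813 for a pairwise t-test with 33 per group, 80% power and alpha 0.017. With a two-sided noncentral t, df = 64 and noncentrality 0.813 × √(33/2) = 3.30, power is 80.0%, and the solved effect size is 0.8129. It reproduces. It concerns the contrast between session categories, so it does not size the bias discussed here.

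**Is a dropout rate given?** Section IV.B.1 expects about 100 eligible per year, 50% attrition and 100 subjects in two years: 100 × 2 × (1 − 0.5) = 100. Section IV.E then says "We expect to recruit 100 patients". The 50% is therefore most naturally loss before recruitment, and loss after enrolment is not stated.

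**Bias formula.** Let d be the share lost. Then

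bias = completers' mean change − mean change of all enrolled = d × (completers' mean change − leavers' mean change).

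Both factors must be assumed. For example, d = 0.1 with a difference of ±0.2 SD gives ±0.02 SD, and d = 0.2 with ±0.5 SD gives ±0.10 SD.

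**Illustration.** These inputs are assumptions, not figures from the documents: 4 visits (baseline and three follow-ups), SD 1 at each visit, equal correlation 0.6, no true change, loss after visit 2 at 10% or 22%, and log-odds of leaving 0.5 to 1.0 per SD of the driving score. The completers' figure is the mean of visit 4 minus baseline over 1,000,000 simulated children, weighted by the probability of staying. The mixed-model figure is the maximum-likelihood estimate under this pattern: regress visit 4 on visits 1 and 2 in completers, then average the prediction over all children. Entries are in SD, for log-odds 0.5 and 1.0.

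| Loss depends on | Loss | Completers | Mixed model |
|---|---|---|---|
| Early worsening (visit 2 minus baseline) | 10% | +0.021, +0.038 | within 0.004 of 0 |
| | 22% | +0.044, +0.079 | within 0.004 of 0 |
| Low baseline score | 10% | −0.018, −0.035 | within 0.004 of 0 |
| | 22% | −0.041, −0.074 | within 0.004 of 0 |
| Low visit-2 score | 10%, 22% | +0.001 | within 0.004 of 0 |
| Low visit-4 score, not seen | 10% | +0.021, +0.038 | +0.028, +0.053 |
| | 22% | +0.044, +0.077 | +0.060, +0.111 |

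If high unseen scores drive loss, the last two rows change sign.

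Check against the formula, early worsening at 22% and log-odds 1.0: all children average 0, so leavers average −0.079 × 0.78/0.22 = −0.280, and 0.22 × (0.079 + 0.280) = 0.079.

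**Sensitivity to the correlation.** With AR(1) correlation instead, completers' bias at 22% loss is +0.058 to +0.106 (early worsening), −0.083 to −0.148 (low baseline) and −0.025 to −0.046 (low visit 2). The mixed model stays within 0.004 SD of zero in these three cases.

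**How far must a delta analysis reach?** Delta needed = mixed-model bias / share lost. From the unseen-score rows: 0.028/0.10 = 0.28, 0.053/0.10 = 0.53, 0.060/0.22 = 0.27 and 0.111/0.22 = 0.50 SD, in either direction. With AR(1) the need rises to at most 0.80 SD. A range of −1.0 to +1.0 SD covers all of these.

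**The case against.** The strongest reply is that the off-study criteria govern participation, not analysis. No section discards earlier scores or defines a completers' set, and the term repeated measures analysis is sometimes used loosely for a mixed model. This stands as far as it goes: the completers' reading follows from the named method in its standard form, not from an explicit statement. If a mixed model is meant, one sentence settles the matter.

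Second, every magnitude rests on assumed loss, correlation and strength of selection, and at 10% loss the bias is small. This stands in full.

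Third, the mixed model is not always better. The working shows it further from the truth than completers when loss depends on unseen scores, and the documents do not say which mechanism applies. This stands, and it is why a delta-adjusted analysis belongs beside it. It does not rescue the named method, which is also biased in that case and is biased as well when loss depends on scores already in hand, where the mixed model is not.

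Fourth, a reader might infer that the low-session category (0 to 3 sessions) would empty out because children must complete 4 time points. The documents do not support that. A completer with 3 sessions falls in that category, and Section IV.B.3 describes infrequently seen children who are given up to 6 months to complete. There is no ground here for downgrading the session-category comparison, which is the only one the plan powers.

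**Conclusion.** The concern holds in a conditional form: followed as named, the primary result is in effect a completers' change, and selective loss would enter it directly. The direction is open and the size is unknown. Under the stated assumptions with equal correlation, the bias is about 0.02 to 0.04 SD at 10% loss and 0.04 to 0.08 SD at 22% for loss driven by early worsening or low baseline, with opposite signs. It is larger under AR(1) correlation.

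Three stronger readings should be resisted. The documents do not say that leavers' data are discarded. They do not give a 50% dropout rate after enrolment. They do not show that the bias favours CAT.

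This should be fixed, because a better method is available at little cost. Confidence is moderate, since the actual loss may be small. The lack of a concurrent comparison, which Section IV.D acknowledges, is a separate limit that the fix does not remove.

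**What to change.** The off-study criteria can stay as they are. The changes are to the analysis.

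1. In Section IV.E, replace repeated measures ANOVA/ANCOVA with a likelihood-based mixed model for repeated measures: visit as a category, unstructured covariance, and baseline as the first repeated measure. Include every child with a baseline and all visits collected before going off study. Keep the planned session-category comparison as stated.
2. Report completers as a sensitivity analysis. Add one delta-adjusted analysis that shifts leavers' imputed 3-month scores down and up, for example from −1.0 to +1.0 SD. That range is a judgement.
3. Tabulate reasons for going off study by visit and baseline score. Show the session-category comparison with and without children who left early.

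Items 1 and 2 cost plan wording and some analysis time, and item 3 is a tabulation from existing records. No new patients or visits are needed. The downside is that the main analysis then assumes missing at random. If loss depends on unseen scores, it can be more biased than completers (in the illustration at 22% loss, about 0.06 to 0.11 against 0.04 to 0.08 SD), hence the delta analysis. If few children left, the result will barely change.

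### The primary outcome is PedsQL at about 3 months, but the plan names only repeated measures ANOVA, with no term or contrast; the default time test does not target 3 months

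*Combined protocol and SAP*

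**What the plan says.** Section IV.E (Data Analysis Plan) ties the primary outcome to one time: "The primary outcome is Peds QL at approximately 3 months". The secondary outcomes (Resilience Scale, Faces Scale, posture) are set at the same time. The method follows: "A repeated measures analysis of variance will be used to analyze the primary and secondary outcomes". An analysis of covariance version may add covariates, and "All of the analysis will be adjusted for baseline measures". The section does not say whether baseline enters as one of the repeated visits or as a covariate.

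Section IV.D (Potential Scientific Problems) explains that there is no control arm and states the comparison: "we will compare the subjects to themselves over time to look at longitudinal changes of CAT".

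Section IV.B.3 (Study Design) schedules testing "before the intervention, and approximately every 30 days for no less than 3 months and a maximum participation of 6 months". Among the Off Study Criteria is "Unable to complete 4 time points in 6 months". Together these imply four assessments: baseline and three follow-ups at least 30 days apart, the last of which may fall as late as 6 months.

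On dose, Section IV.B.3 says that it "will be recorded (number and type of sessions) and will be factored into the analysis", without giving its role in the model. The power paragraph of IV.E compares three session-count groups pairwise.

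**The concern.** An outcome at one time calls for one comparison: PedsQL at about 3 months against baseline. A repeated measures ANOVA on one group gives, by default, a test of whether the visit means differ at all. With baseline as a visit this has 3 degrees of freedom; with baseline as a covariate and three follow-ups it has 2. It rejects for a difference at any visit, in either direction, and gives no estimate of the 3-month change.

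If that p-value is taken as the primary result, a temporary change that has gone by 3 months can be reported as a positive finding on the primary outcome. The 2-df form has the opposite fault as well: an improvement that appears by the first follow-up and stays constant produces no difference among the follow-ups, so the time test cannot detect it.

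**Working it through.** **1. The plan's own figure.** The power paragraph gives a minimum effect size of 0.813 for 33 per group, 80% power and alpha 0.017. A two-sided two-sample t-test with df = 2 × 33 − 2 = 64 and noncentrality d × √(33/2) reaches 80% power at d = 0.8129, so the figure reproduces. It describes a comparison between session-count groups and says nothing about a test of change over time.

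**2. Inputs.**
- From the documents: four time points (IV.B.3) and n = 100 (IV.E).
- Assumed, because the documents give no values: SD 1 at each visit; equal correlation ρ of 0.3, 0.5 or 0.7 between visits; a dip d of 0.1, 0.2 or 0.3 SD at the first follow-up only; two-sided 0.05.
- n = 50 is an assumed lower case, should the 50% attrition in IV.B.1 apply to the 100 recruited. IV.B.1 itself reads as if attrition is already taken off: 100 × 2 years × 0.5 = 100.

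**3. Four-visit time test.** The visit means are (0, −d, 0, 0), so the true 3-month change is zero. The grand mean is −d/4 and the sum of squared deviations is 0.75d². The noncentrality is

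λ = n × Σ(μⱼ − μ̄)² / (1 − ρ) = 0.75 n d² / (1 − ρ), with 3 and 3(n − 1) df.

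For n = 100, d = 0.3, ρ = 0.5: λ = 0.75 × 100 × 0.09 / 0.5 = 13.5 on 3 and 297 df, which gives 87.9%.

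Percentage of trials with a significant time test:

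| n | ρ | d = 0.1 | d = 0.2 | d = 0.3 |
|---|---|---|---|---|
| 50 | 0.3 | 8.3 | 19.9 | 41.6 |
| 50 | 0.5 | 9.7 | 26.8 | 56.0 |
| 50 | 0.7 | 13.2 | 43.0 | 80.2 |
| 100 | 0.3 | 12.0 | 37.8 | 73.8 |
| 100 | 0.5 | 15.1 | 51.2 | 87.9 |
| 100 | 0.7 | 23.0 | 75.5 | 98.6 |

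Only d² enters λ, so a temporary rise of the same size gives the same figures.

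**4. Baseline-to-3-month contrast on the same data.** Its true value is zero. In simulation (10,000 runs per setting, d = 0.3, n = 50 and 100, ρ = 0.5 and 0.7) it rejected in 4.7% to 5.0%. In those settings the time test was significant and the contrast was not in 51% to 94% of trials.

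**5. Baseline as a covariate, three follow-ups repeated.** For means (−d, 0, 0), λ = (2/3) n d² / (1 − ρ) with 2 and 2(n − 1) df. For n = 100, d = 0.3, ρ = 0.5: λ = 12.0, which gives 87.8%. Across n = 50 to 100 and ρ = 0.5 to 0.7 the range is 57% to 98%. With a constant 0.3 SD improvement at all three follow-ups, this test rejects in only about 5%.

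**6. Dose-group reading.** With three groups of 33, four visits, ρ = 0.5 and a 0.3 SD dip shared by all groups, simulation gave 5.3% for the dose effect and 4.9% for dose by time. A shared dip does not inflate either test.

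**7. Price of the contrast.** For a constant 0.3 SD improvement at n = 100 and ρ = 0.5, the contrast has noncentrality 0.3 × √100 / √(2 × 0.5) = 3.0 and 84% power, against 88% for the four-visit time test.

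**The case against.** The strongest reply is that the plan names a model family and no term. A reader might infer that the sponsor chose the overall time test as the primary test. The documents do not say so, and a repeated measures ANOVA can carry a baseline-to-3-month contrast. This stands: the defect is that no contrast is specified and the default does not fit the outcome.

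Second, the power paragraph and the dose sentence in IV.B.3 point to a comparison by number of sessions. If dose or dose by time is the tested term, the percentages in the table do not apply. This also stands and limits the point to the time-effect reading. Section IV.D supports that reading, and the dose-group text does not define a 3-month contrast either.

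Third, a reader might infer from the vincristine and steroid toxicities in Section II that an early dip with recovery is to be expected. Section II gives no timing and no recovery by 3 months, and the baseline is before CAT, which need not be before chemotherapy. The dip is therefore only an illustration.

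Fourth, a reader might infer that unequal correlation between visits seriously distorts the ANOVA's significance level. The documents give no correlations. Under assumed fading correlation of 0.7 to 0.8 between adjacent visits, the simulated level was only 0.061 to 0.067. The point does not rest on this.

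Adjustment for baseline is no answer, as step 5 of the working shows.

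**Conclusion.** The point holds in a limited form. The plan fixes the primary outcome at about 3 months and does not name the comparison that would answer it. Run by default in one group, the stated method gives a non-directional test across all visits, which can be significant with no 3-month change.

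How often depends on quantities the plan does not give. Over the assumed range it runs from 8%, little above the nominal 5%, to 99%. The 88% at n = 100, correlation 0.5 and a 0.3 SD dip is one point in that range and should not be quoted alone. The mismatch between test and outcome does not depend on any of these assumptions; only its size does.

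Even the right contrast would not separate an effect of CAT from the course of illness and treatment, because there is no control arm. That is a separate limitation. The sponsor should correct this point, and can do so with data already being collected.

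**What to change.** In Section IV.E:

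1. State that the primary test is the single baseline-to-3-month change in PedsQL, reported as an estimate with its own standard error and 95% CI, and give its alpha. The only alpha now in the plan, 0.017, belongs to the dose-group power calculation.
2. Define the range of days after baseline that counts as about 3 months, and say how a fourth assessment outside it is handled. IV.B.3 lets the time points stretch to 6 months, so the fourth assessment is not always a 3-month assessment.
3. Treat the overall time test and the intermediate visits as descriptive.
4. Specify the same contrast for each secondary outcome.
5. State that the comparison of session-count groups is a separate analysis and that the 0.813 calculation refers to it.

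The protocol says that enrolment was reached in 2019, so the change should be dated and should say whether outcome data had been examined.

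The cost is wording in one section and no extra data. The contrast has slightly less power for some patterns of change, such as the 84% against 88% shown in the working.

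### Adjusting every analysis for baseline conflicts with using baseline as each child's control: read in the usual way, 3 months is never tested against baseline

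*Combined protocol and SAP*

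**What the plan says.** Section IV.B.3 (Study Design) sets the comparator: "A repeated measures design will be used with each patient serving as his/her own control". Section IV.D (Potential Scientific Problems) explains that randomisation is ruled out because CAT is standard of care, and concludes that "we will compare the subjects to themselves over time to look at longitudinal changes of CAT". Aim (a) in Section I asks whether CAT improves the child's reported quality of life.

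Instruments are given before the intervention and then "approximately every 30 days for no less than 3 months and a maximum participation of 6 months". One off-study criterion is "Unable to complete 4 time points in 6 months".

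Section IV.E says "The primary outcome is Peds QL at approximately 3 months" and "A repeated measures analysis of variance will be used to analyze the primary and secondary outcomes". It adds an analysis of covariance with further covariates, then closes the paragraph with "All of the analysis will be adjusted for baseline measures". It does not say whether baseline is a covariate, a response visit or the reference for a change score, or which model term is the primary test. The next paragraph powers a different contrast: pairwise comparisons among children with low, intermediate and high numbers of CAT sessions.

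**The concern.** In a single-group, own-control design the pre-CAT score is the control. A rule that makes it an adjustment variable in every analysis, with no exception for the before-after analysis, takes the comparator out of the comparison if followed in the ordinary way. The remaining time effect asks whether the follow-up visits differ among themselves. A benefit that appears early and lasts, which would be a good result for CAT, leaves no trace in that test.

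An analyst who notices this and puts baseline back as a response while keeping it as a covariate can meet a second problem, a test of mean change that is too liberal. The choice among these models affects the answer to aim (a), and the plan leaves it open until the data are in hand.

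**Working it through.** **The plan's own figure.** Section IV.E gives a minimum effect size of 0.813 for 33 children per group, 80% power and alpha 0.017. A two-sample t-test (noncentral t, 64 df, two-sided) gives 0.8129, so the figure reproduces. It concerns dose groups. The documents give no figure for the before-after test.

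**Inputs.** The expected sample is 100 children (IV.B.1 and IV.E); 50 is added as a lower case. Four time points come from the off-study criteria, taken here as baseline plus three follow-ups, because the plan does not say whether baseline is one of the four. The documents give no SD or between-visit correlation. I therefore work in SD units and assume equal correlation ρ between visits, normal scores, complete data and two-sided 5% tests. The 0.4 SD effect is also an assumption.

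**Reading 1: baseline as covariate, follow-ups as responses.** For the repeated measures time test, the noncentrality is λ = N Σ(μj − μ̄)² / (1 − ρ).

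- Step gain, follow-ups only: means 0.4, 0.4, 0.4. The sum of squares is 0, so λ = 0 and the test rejects at its nominal 5% whatever N and ρ are.
- Step gain, baseline as a response: means 0, 0.4, 0.4, 0.4, with mean 0.3. The sum is 0.09 + 3 × 0.01 = 0.12, so λ = 0.12N/(1 − ρ).
- Linear rise to 0.4, follow-ups only: means 0.133, 0.267, 0.4. The sum is 2 × 0.133² = 0.0356, so λ = 0.0356N/(1 − ρ).
- Paired 3-month minus baseline t-test, either shape: noncentrality 0.4√N / √(2(1 − ρ)).

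| N | ρ | Step: follow-ups only | Step: baseline as response | Linear: follow-ups only | Paired test, either shape |
|---|---|---|---|---|---|
| 50 | 0.3 | 5% | 67% | 27% | 65% |
| 50 | 0.5 | 5% | 83% | 36% | 79% |
| 50 | 0.7 | 5% | 97% | 56% | 95% |
| 100 | 0.3 | 5% | 95% | 50% | 92% |
| 100 | 0.5 | 5% | 99% | 66% | 98% |
| 100 | 0.7 | 5% | >99.9% | 87% | 99.9% |

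Simulation at N = 100 agrees for the step gain: 4.9-5.3% for follow-ups only, and 94.5-100% with baseline as a response.

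**Reading 2: baseline as a response and as a mean-centred covariate crossed with time.** With no true change and N = 100, the simulated false-positive rate is 8.5%, 8.0%, 6.2% and 5.6% at ρ = 0.3, 0.5, 0.7 and 0.8. At N = 50 it is 9.3%, 7.4%, 5.8% and 6.0%. The two-visit form shows why. If 3-month change is regressed on centred baseline and the intercept is tested, the estimate is the mean change, but its standard error uses the residual variance 1 − ρ² in place of 2(1 − ρ). The standard error is too small by the factor √((1 + ρ)/2), so the error rate is 2[1 − Φ(1.96√((1 + ρ)/2))]. That is 11.4%, 9.0%, 7.1% and 6.3% at the same four correlations.

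**Reading 3: baseline as a response and as an additive covariate in classical repeated measures ANOVA, complete data.** A covariate that is constant within a child is absorbed by the between-child stratum. In a check dataset the time F was 0.3613 with and without it, and the simulated error rate was 4.5-5.3%.

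**Reading 4: unadjusted change from baseline, or baseline as a response only.** The contrast is kept. The simulated error rate of the four-visit time test at N = 100 is 4.5-5.1%.

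**Reading 5: dose-group comparison with baseline as covariate.** This is ordinary analysis of covariance. With 33 per group and dose unrelated to outcome, the simulated error is 1.6-1.8% per pair and 4.3-4.6% familywise, as planned.

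**The case against.** The strongest reply is that the sentence need do no harm. Readings 3 and 4 comply with it, keep the before-after contrast and hold the error rate. The only contrast the plan powers is the dose comparison in the paragraph that follows, where adjusting for baseline is right; if that is the primary test, the sentence is correct for it. The 5% rejection rate also depends on the whole gain arriving by month 1. All of this stands.

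Two stronger readings are therefore not supported. A reader might infer that the primary test must either lose the before-after contrast or have the wrong error rate. It need not, because the list of harmful readings is not exhaustive and the plan does not name the primary contrast. A reader might also infer a very high false-positive rate, by imagining an uncentred baseline score crossed with time, so that the time effect is tested at a score of zero. The plan mentions no such interaction, and that result would be a coding error rather than a consequence of the sentence.

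The reply does not remove the conflict. The additive covariate is harmless because it does nothing to the time test, which is no reason to require it. The own-control justification in IV.B.3 and IV.D, together with aim (a), makes the before-after question a stated purpose even if dose is the powered contrast. The sentence covers both analyses, which need baseline handled differently.

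**Conclusion.** The concern holds in a limited form. A stated blanket rule, read in the most usual way, leaves the own-control question untested for an early, sustained gain: about 5% rejection against about 65-100%. For a linear rise it costs power: 27-87% against 65-99.9% for the paired test. One attempt to restore baseline as a response gives a false-positive rate of about 6-9%. Other readings are sound, and the dose analysis is unaffected.

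The sizes rest on an assumed 0.4 SD effect, correlations of 0.3-0.7 (up to 0.8 for the error rates), equal correlation between visits, normal scores and complete data. The result for the step gain does not depend on the correlation: with no baseline visit among the responses there is nothing for the test to detect. This goes beyond missing detail and should be settled before analysis.

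**What to change.** Replace the closing sentence of that paragraph in IV.E with rules along these lines:

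1. Own-control analysis: a repeated measures model with baseline as one of the response visits and no baseline covariate. The test is the 3-month minus baseline contrast. State the time levels and the covariance structure.
2. Dose analysis: follow-up scores as responses, number of CAT sessions as the factor of interest, and the centred baseline score as covariate.
3. State which of the two is the primary test.

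The cost is a few sentences. All the scores needed are already collected under IV.B.3, and no further children or visits are required.
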